5.4 Other Outcomes of Interest

A comparison between CCTA and TEE at 45 days and then at 13 months will be performed in order to obtain a validation of CCTA to reveal the LAA patency.

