9.1.3 Post procedure management and hospital discharge

After the procedure, patients will receive ASA and clopidogrel or (N)OAC at discretion of the treating physician (according to the bleeding risk, the stroke risk and intra-procedural TEE evaluation) for 45 days and then will undergo TEE assessment (as per standard of care):

- If a residual peridevice leak flow > 5 mm or a intracardiac thrombus is detected, treatment with ASA and (N)OAC should be considered up a sequential TEE evaluation at 6 months. Final decision to implement an OAC regimen with or without ASA will eventually be left to the discretion of the treating physician taking the ischemic ad bleeding risk into account;
- If residual peridevice leak flow ≤ 5 mm is detected, patients will receive ASA and clopidogrel or (N)OAC (at discretion of the treating physician according to the bleeding and stroke risk) up until 3 months after procedure. Thereafter, monotherapy with ASA will be continued until 12 months after procedure.

These drug regimens are recommended according the current evidence and the instructions for use of the two devices (Appendix 2).

The following evaluations will be performed at up to 48 h after the procedure or at hospital discharge whichever comes first:

- Physical examination as defined in 9.1.6
- Measurement of vital signs as defined in 9.1.5
- Collection of concomitant therapy and assessment of any additional intervention, if any, which occurred after LAAC
- Assessment of SAE and AESI as defined in 11.1 and Appendix 1
- 12 lead ECG
- Routine laboratory tests within 48 hours prior to the index procedure as defined in 9.1.7
- A transthoracic echocardiogram is encouraged (but not mandated) before the discharge in order to detect pericardial effusion and for the assessment of the post-procedure positioning of the LAA device.

9.1.4 45 days, 6month, 13 month, 2/ 3/ 4/ 5 year follow up

Patients will be followed-up with hospital visits at after 45 days(primary endpoint assessment) and thereafter at 6 and 13 months as well as after 2, 3, 4 and 5 years the index procedure. In case of impossibility to have an in hospital visit, a phone call to the patient and/or to the general practitioner will be performed (except for the 45 days visit).

The following evaluations will be performed at follow up visits:

- Collection of medical history
- Physical examination as defined in 9.1.6
- Measurement of vital signs as defined in 9.1.5
- Collection of concomitant therapy

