- Assessment of SAE and AESI as defined in 11.1 and Appendix 1
- 12 lead ECG
- TEE will be performed at 45 days. TEE could be repeated at 6 and 13 months after procedure if clinically indicated (in case of an intra-cardiac thrombus or/and a PDL >5 mm are revealed at 45 days) according to current standard of care
- CCTA at 45 days and at 13 months after procedure will be performed as study specific interventions.

In the event of pandemic or any other condition for which the participation to follow-up visits would put at risk the health of the patients and/or of the medical staff, the hospital visits will be replaced by phone call. Furthermore, the performance of imaging follow-up outside of protocol temporal window will be allowed.

If a phone call is performed instead of an hospital visit, the following data will be collected:

- Vital status
- Assessment and reporting of adverse clinical events as defined in 9.1.8 and Appendix 1
- Assessment and reporting of SAEs and AESI
- Assessment and reporting of pharmacotherapy, and additional interventions received since last contact.

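### Section 5.4 plans to validate CCTA against TEE at 13 months, but the 13-month TEE is provided only for patients selected on their 45-day findings

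*Combined protocol and SAP*

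**What the plan says.** Protocol section 5.4 sets the aim: "A comparison between CCTA and TEE at 45 days and then at 13 months will be performed", with validation of CCTA as the stated purpose.

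Section 9.1.4 sets who is scanned. For CCTA: "CCTA at 45 days and at 13 months after procedure will be performed as study specific interventions". For TEE at the first visit: "TEE will be performed at 45 days". For later TEE: "TEE could be repeated at 6 and 13 months after procedure if clinically indicated", with the indication given in brackets as "in case of an intra-cardiac thrombus or/and a PDL >5 mm are revealed at 45 days".

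The study schedules in the protocol and in SAP section 2.7 agree. Both 13-month imaging entries stand in brackets, but the CCTA footnote marks it as study-specific while the TEE footnote makes it conditional on clinical indication.

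Section 9.1.4 does not name the test that must show the leak or thrombus. Section 9.1.3 has patients treated "for 45 days and then will undergo TEE assessment (as per standard of care"), and the rule that begins "If a residual peridevice leak flow > 5 mm or a intracardiac thrombus is detected" follows directly under that TEE. Section 8.7 has the same structure. Section 6.1 also places the rule under the TEE but mentions CCTA alongside. Device-related thrombus is read on both tests (Appendix 1, 17.11).

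**The concern.** A comparison meant to validate one test against another needs both tests in a sample whose make-up does not depend on what the tests showed. That holds at 45 days, where both are planned in every patient. It does not hold at 13 months. A patient whose appendage was patent on the 45-day CCTA but who had no large leak or thrombus has no protocol indication for a second TEE. These discordant patients are the protocol's stated reason for preferring CCTA (section 3.1), and the 13-month pairs would largely leave them out.

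At stake is whether 13-month specificity, relative detection rates or agreement could be read as properties of CCTA in the implanted population. Section 3.6 calls replacing TEE with CCTA desirable, so a 13-month validation claim from such a subset could be taken further than it can bear.

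**Working it through.** **Plan's own figure.** There is none for this comparison: no number of pairs, no precision and no method. The 200-patient calculation concerns the primary endpoint and does not enter.

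**Who has which test (protocol 9.1.4 and schedule).**

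| | CCTA | TEE |
|---|---|---|
| 45 days | all patients | all patients |
| 13 months | planned for all, study-specific | optional, after thrombus and/or leak above 5 mm at 45 days |

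**Number of pairs.** The documents give no rate of large leak or thrombus at 45 days. Assume 2%, 5% or 10% of 200, all rescanned: 4, 10 or 20 pairs. For an assumed true proportion of 80%, the 95% half-width is 1.96 × √(0.8 × 0.2 / n):
- n = 4: 39 points
- n = 10: 25 points
- n = 20: 18 points

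The normal approximation is rough at these sizes and serves only for scale.

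**Illustration A: complete selection.** Section 3.1 cites a 23-patient series: 52% patent on CT (12/23), 34% on TEE (taken as 8/23), and 58% of CT-patent cases seen on TEE (7/12). Hence both positive 7, CT only 5, TEE only 1, neither 10. Keep only the 8 TEE-positive patients and assume unchanged findings.

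| | All 23 | 8 TEE-positive |
|---|---|---|
| Raw agreement | 17/23 = 74% | 7/8 = 88% |
| Chance agreement | (12×8 + 11×15)/23² = 261/529 | (7×8 + 1×0)/8² = 7/8 |
| Kappa | (391 − 261)/(529 − 261) = 0.485 | 0 |
| CT-positive among TEE-positive | 7/8 | 7/8 |
| TEE-positive among CT-positive | 7/12 = 58% | 7/7 = 100% |
| CT-negative among TEE-negative (specificity) | 10/15 = 67% | not estimable (0 patients) |

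**Illustration B: partial selection.** Apply similar rates to 200 patients: TEE-positive 34%, CT-positive 52%, and CT-positive among TEE-positive 0.90 (the series implies 0.52 × 0.58 / 0.34 = 0.89). The cells are both 61.2, TEE only 6.8, CT only 42.8, neither 89.2. Assume a 13-month TEE in 15% of those who would then be TEE-positive and in 1% of those who would be TEE-negative. The cells become 9.18, 1.02, 0.43 and 0.89, which is 11.5 pairs.

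| | All 200 | Selected |
|---|---|---|
| CT minus TEE detection | +18 points | −5 points |
| Raw agreement | 75% | 87% |
| Kappa | 0.51 | 0.48 |
| TEE-positive among CT-positive | 59% | 96% |
| TEE-negative among CT-negative | 93% | 47% |

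Four other settings were tried. Three used rescanning rates of 6% and 1%, 15% and 3%, and 29% and 0.5%. The fourth used 15% and 1% with CT positivity set to 99% in TEE-positives and 60% in TEE-negatives. Over all five, the detection difference ran from −9 to +6 points, raw agreement from 84% to 92%, and kappa from 0.25 to 0.59. In the main setting specificity is 89.2/132 = 68% by construction, but the selected sample would estimate it from 132 × 0.01 = 1.3 expected TEE-negative patients.

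**The case against.** The strongest reply is that the rest of the plan already keeps the TEE comparison at 45 days. Section 4.3 and the secondary outcomes in 5.2 list TEE at 45 days only. Sections 9.2 and 17.13 compare 45-day CCTA with 45-day TEE. The SAP's imaging table (5.8) covers 45 days, and the SAP describes no 13-month CCTA-TEE analysis. This is right, and it makes 5.4 the outlier. But none of these places withdraws the 13-month validation that 5.4 announces.

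A reader might also infer that the design would make TEE look fully sensitive and agreement far better. The documents do not support that:
- The 100% in illustration A follows from keeping only TEE-positives and assuming no change. It selects on any TEE leak, whereas 9.1.4 requires more than 5 mm or a thrombus.
- Leaks change. In a 25-patient series in section 3.1, the two patients with major leaks after deployment had none significant at follow-up, and the two with major leaks at follow-up had none significant after deployment.
- Raw agreement rises, but kappa can fall to zero.
- CCTA detection among TEE-positives, the sensitivity figure if TEE is the reference, stays at 7/8.

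Nor is this verification bias in its usual form, where the index test decides who gets the reference test. Here selection is on findings about 11 months earlier, mainly from the reference test. A thrombus seen first on CCTA might also lead to a repeat TEE; the sample would still be selected on the tests being compared.

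**Conclusion.** The point holds, at minor severity. Section 5.4 announces a 13-month validation that the imaging plan in 9.1.4 and the schedules cannot support. The pairs would be few and selected on earlier results of the tests compared, with little information on patients who were TEE-negative at 45 days. Specificity, relative detection rates and agreement from them could not be generalised to the implanted population.

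The size cannot be fixed. It depends on the unknown rate of large leak or thrombus, on how many of those patients have the optional TEE, and on how leaks evolve. The 4 to 20 pairs and the illustrated shifts rest on the assumed rates shown, and no single direction of bias can be claimed.

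A reader might go further and doubt the CCTA primary endpoint or the whole CCTA-TEE comparison. The documents give no ground for that: the primary endpoint uses CCTA without the 13-month TEE, and both tests are planned in all patients at 45 days.

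**What to change.** Reconcile sections 5.4 and 9.1.4. In 5.4, limit the validation of CCTA against TEE to 45 days, in line with 9.2 and 17.13. Add that any 13-month CCTA-TEE pairs will be reported descriptively, with the number of pairs and the rule by which patients came to have a 13-month TEE, and that no validation claim will be drawn from them. Mirror this in the SAP if 13-month imaging tables are added.

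The cost is a sentence or two. No scan, visit or indication for TEE changes, and the SAP loses no analysis, since it specifies none for this comparison at 13 months.

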5.5 Safety Outcomes

Main safety outcomes are:

- Bleeding Academic Research Consortium (BARC) bleeding grade 2, 3 and 5 at up to 48 hours or discharge whichever comes first and 45 days
- Net adverse clinical events (NACE) defined as the composite of death, fatal and non-fatal stroke, peripheral embolization and BARC 2, 3, or 5 at up to 48 hours or discharge whichever comes first and 45 days
- Device related thrombosis at 45 day TEE/CCTA and 13-month CCTA in the per protocol and as treated populations

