5.2 Secondary Outcomes

Secondary end-points include¹:

- LAA patency (arterial and/or venous phase) at 45-day and 13-month CCTA in the per protocol and as treated populations
- All cause of death, stroke, systemic or pulmonary embolism and spontaneous MI
- Cardiovascular death
- Ischemic stroke
- Haemorrhagic stroke
- Bleeding events according to the BARC classification at each follow up.
- Procedure-related complications²
- Rate of patients on (N)OAC at 45 days and 6 months
- Device related thrombosis (DRT) at 45 day TEE/CCTA and 13-month CCTA in the per protocol and as treated populations
- Feasibility outcome (number of device implantation attempts, total time procedure, x-ray dose and total contrast dose used in the procedure)
- LAA patency at 45 day TEE in the per protocol and as treated populations

Adverse clinical events will be assessed at up to 48 hours or discharge whichever comes first, at 45 days, and yearly.

¹ For the definitions of endpoint and adverse clinical events see the Appendix 1.

²As defined in 5.3.

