6. STUDY DESIGN

6.1 General study design and justification of design

This will be a multicentre, open-label, prospective, randomized study in patients with AF and an indication for anticoagulant therapy with high bleeding risk, that agree to the LAAC procedure. Patients will be submitted to a screening protocol in a period not greater than 90 days before procedure, including medical and drug history, physical examination, 12-lead ECG, CCTA (as per standard of care) and TEE if clinically indicated.

Once the patient is judged eligible and the informed consent has been signed, the patient will be randomly assigned in a 1:1 to receive a LAAC with Amplatzer Amulet or Watchman/FLX device. In the event that the patient is randomized to the Watchman/FLX arm, the operator will be able to choose, on the basis of clinical reasons, if to implant Watchman or the new generation Watchman FLX (if available in the center).

Sizing device and implantation will be performed according to common practice guidelines⁵ (and so based on both preprocedural CCTA and intraprocedural TEE-angiography images). Furthermore, as recommended by the recent consensus document,⁵ the first operator will be able to choose if use intracardiac echocardiography (ICE) instead of TEE to guide the procedure, on condition that a TEE evaluation is performed within 2 days before the procedure (in order to exclude LAA thrombus, to confirm the LAA suitability for both devices and to make the device sizing). Angiography at the end of the procedure is recommended to assess PDL. In case of concomitant procedure during LAAC, it will be reported separately in term of duration time, contrast dose and x-ray dose.

At the end of procedure, a measure of PDL must be provided.

A transthoracic echocardiogram is encouraged (but not mandatory) before the hospital discharge in order to detect pericardial effusion.

All patients randomly allocated to the Watchman/FLX or Amulet arm will receive acetylsalicylic acid (ASA) and clopidogrel or (N)OAC (at discretion of the treating physician and according to the bleeding risk, stroke risk as well as based on post-procedural TEE evaluation) for 45 days and then will undergo TEE assessment (as well as CCTA):

- If a residual peri-device leak flow at 45 days > 5 mm or a intra-cardiac thrombus is detected, a therapy with ASA and (N)OAC could be considered up a sequential TEE evaluation at 6 months.

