2.8 Blinding

Allocation to the two randomized devices Amulet vs Watchman/FLX is concealed. After the randomization result is available, the study personnel, monitors, the trial statistician receiving the raw data download are not blinded to the randomized device.

However, independent blinded analyses will be conducted by a second statistician who does not know the allocation result of the randomization (e.g. coded X vs Y). Moreover, also the clinical event adjudication committee adjudicating the events is blinded to the randomized device.

The Sponsor will be provided with blinded tables of the primary outcome analyses (e.g. coded X vs Y with no denominators), which the Sponsor can use for final plausibility checks and queries for e.g. outliers to be send to the centres. If this final cleaning process is performed, the Sponsor will receive the unblinded results.

CTU Bern	Swiss APERO SAP	Version: 2.0	
	Template: CS_STA_TEM-11	Valid from: 17.08.2021	

3. Data management

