3.2 Data validation

Before locking, the data will be checked for completeness using e.g. missing tables functions. The plausibility of the primary and secondary outcomes will be checked using outlier analyses and histograms, and will be queried if they are outside the expected range, including dates of events. Only events occurring after the implantation (attempt) of the LAAC device will be analysed, in case no LAAC procedure was started the randomization date will be used instead.

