6.1.3 Safety outcome

The main safety outcomes are:

- *Bleeding Academic Research Consortium (BARC) bleeding grade 2, 3 and 5 up to 48 hours or discharge whichever comes first and 45 days*

CTU Bern	Swiss APERO SAP	Version: 2.0	
	Template: CS_STA_TEM-11	Valid from: 17.08.2021	

- *Net adverse clinical events (NACE) defined as the composite of death, fatal and non-fatal stroke, peripheral embolization and BARC 2, 3, or 5 up to 48 hours or discharge whichever comes first and 45 days*
- *Device related thrombosis at 45 day TEE/CCTA and 13-month CCTA in the per protocol and as treated populations*

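### The early count of BARC 2/3/5 bleeding and NACE stops at discharge if that precedes 48 hours, so its length depends on a post-randomization event and conflicts with the 48-hour window in the safety objective

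*Combined protocol and SAP*

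**What the plan says.** Protocol 5.5 lists three main safety outcomes. Two are clinical, and both carry an early and a later time point. The first is BARC "bleeding grade 2, 3 and 5 at up to 48 hours or discharge whichever comes first and 45 days". The second, NACE, is a composite of death, stroke, "peripheral embolization and BARC 2, 3, or 5 at up to 48 hours or discharge whichever comes first and 45 days". SAP 6.1.3 carries the rule over for bleeding ("bleeding grade 2, 3 and 5 up to 48 hours or discharge whichever comes first and 45 days") and for NACE ("BARC 2, 3, or 5 up to 48 hours or discharge whichever comes first and 45 days"). The third outcome, device-related thrombosis, is read from imaging and is not affected.

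Protocol 5.2 uses the same cut-off for event assessment: "Adverse clinical events will be assessed at up to 48 hours or discharge whichever comes first, at 45 days, and yearly". Protocol 9.1.2 and 9.1.3 use it for event collection and for the post-procedure visit.

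Protocol 6.1 states the design: "This will be a multicentre, open-label, prospective, randomized study in patients with AF". SAP 2.8 adds that, once the allocation is known, "the study personnel, monitors, the trial statistician receiving the raw data download are not blinded to the randomized device". The same section says that the committee adjudicating events is blinded.

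Protocol 4.4 sets the safety objective in terms of procedure complications over 48 hours counted from randomization and mentions no discharge cut-off.

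**The concern.** A window that ends at discharge is set by something that happens after randomization. A bleed at 36 hours enters the early count of a patient kept for two days, but not of a patient sent home at 24 hours. If one device group tends to go home sooner, that group is observed for less time and can show fewer early bleeds and NACE with no real difference between devices. Neither document gives discharge criteria, a standard length of stay, or an adjustment for stay. Blinded adjudication protects how an event is classified. It does not protect how long each patient is observed.

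There is also a plain inconsistency. The safety objective and the safety outcomes describe the early period with different end rules and different starting points. An analyst programming the early safety comparison would have to choose between them.

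**Working it through.** **Plan's own figure.** There is none for the early safety outcomes. The only stated power (above 80%, protocol 12.2 and SAP 2.3) concerns the primary endpoint. It reproduces at 82.8% with a two-sided normal approximation, 100 per arm, 50% vs 30%. It has no bearing here.

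**The windows side by side.**

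| Place | What is counted | Start | End |
|---|---|---|---|
| Protocol 4.4 | Procedure complications | Randomization | 48 h |
| Protocol 5.5, SAP 6.1.3 (early) | BARC 2/3/5; NACE | Not stated there; SAP 3.2 implies the implantation attempt, or randomization if no procedure was started | 48 h or discharge, the earlier |
| Protocol 5.3 | Procedure-related complications, including bleeding | Procedure | 7 days |
| Protocol 5.5, SAP 6.1.3 (later), with SAP 3.3 | BARC 2/3/5; NACE | Procedure, or randomization if none was initiated | Day 45 |

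Only the second row has an end that varies between patients. The first and second rows differ in both start and end.

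**Illustration of size.** The documents give no discharge times and no early event rates, so every input here is an assumption. Both arms have the same true risk, a share *f* of an arm leaves at 24 h, the rest are observed to 48 h, and discharge is unrelated to event risk.

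*Constant hazard.* Mean window = 24*f* + 48(1 − *f*).
- *f* = 0.40: 9.6 + 28.8 = 38.4 h
- *f* = 0.60: 14.4 + 19.2 = 33.6 h; ratio 33.6/38.4 = 0.875
- *f* = 0.70: 16.8 + 14.4 = 31.2 h; ratio 31.2/38.4 = 0.8125

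*Front-loaded risk, with 80% of the 48 h risk in the first 24 h.* Share captured = 0.8*f* + (1 − *f*) = 1 − 0.2*f* (small-risk approximation).
- *f* = 0.40: 0.92
- *f* = 0.60: 0.88; ratio 0.88/0.92 = 0.96
- *f* = 0.70: 0.86; ratio 0.86/0.92 = 0.93

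*Absolute scale, wider splits.* For a true 48 h risk *R*, the 24 h risk is *r* = 1 − (1 − *R*)^*w*, with *w* = 0.5 (constant) or 0.8 (front-loaded). The observed proportion is *f r* + (1 − *f*)*R*. With *R* = 10%, *w* = 0.5 and early discharge of 20% vs 80%, *r* = 1 − 0.9^0.5 = 5.13%. The arms then show 9.0% vs 6.1%, a gap of 2.9 points. Over *R* = 5%, 10% and 15%, with 20% vs 50% or 80% discharged early, the gap runs from 0.3 to 4.3 points and the ratio from 0.94 to 0.67.

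*Equal f in both arms.* The ratio is 1 and the gap 0 in every case.

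**The case against.** The strongest reply is that nothing is lost. The same two outcomes are counted again at 45 days over a window that SAP 3.3 fixes for everyone. Procedure-related complications, including bleeding, stroke and death, have a fixed 7-day window (protocol 5.3), and SAP 6.5 lists 7 days among its tabulation periods. A reader might infer that early bleeds drop out of the safety data. They do not, and this limits the point to the early time point.

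A reader might also infer that the early outcomes will be compared as simple proportions. The documents do not say so. Protocol 12.4 gives Kaplan–Meier and log-rank methods for safety endpoints, and SAP 4.1 keeps them for time-to-event endpoints. If patients were censored at discharge and discharge were unrelated to remaining risk, those methods would allow for unequal observation. Fisher tests are specified for the 45-day outcome table and the periprocedural table. No table shell covers BARC 2/3/5 or NACE at 48 hours or discharge. SAP 6.5 does list hospital discharge as a separate tabulation period, without a test. How the early count is analysed is therefore open.

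Third, the phrase may only name the post-procedure visit. That is plausible for protocol 5.2, 9.1.2 and 9.1.3. It does not remove the problem in 5.5 and SAP 6.1.3, because an outcome taken at that visit still covers a shorter period in a patient who leaves early.

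Finally, nothing in the documents shows that the arms differ in discharge time, or who decides on discharge. Influence by staff who know the device is possible under the open-label design, but it is not documented. This stands as a limit on size.

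**Conclusion.** The point holds in a limited form. Two of the three main safety outcomes have an early window that can end at discharge, and this window does not match the safety objective in protocol 4.4. Unequal observation between arms is possible under the rule as written. The documents do not support the stronger conclusion that the arms will differ or that the early results will be biased.

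The size is unknown. The ratios of 0.81–0.88 and 0.93–0.96 rest on assumed discharge splits of 60–70% vs 40% and on the assumed timing of risk. The milder pair applies if early events cluster in the first 24 hours. The primary endpoint, device-related thrombosis, and the 7-day and 45-day safety counts are unaffected, and no powered comparison depends on the early count. The mismatch with protocol 4.4 needs reconciling even if discharge times turn out to be the same.

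**What to change.** In protocol 4.4, 5.2 and 5.5 and in SAP 6.1.3, count the early safety outcomes over one fixed window for every patient: 0–48 hours, whether or not the patient has been discharged. If the case report form holds event dates without clock times, use the equivalent calendar days. Start the window at the LAAC procedure, or at randomization if no procedure was started. This follows SAP 3.2 and 3.3 and leaves no randomized patient without a start time. The post-procedure visit can stay where it is, since only the counting rule changes. Report time to discharge by arm, so that a reader can judge any difference in stay.

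The cost is rewording and one derived variable, and discharge practice does not change. The small downside is that events between discharge and 48 hours rely on reported dates. That dependence is limited. Protocol 11.2 starts SAE and AESI reporting at randomization, with SAEs due within 24 hours and AESIs within 10 days of awareness. SAP 3.2 says that implausible outcome data "will be queried if they are outside the expected range, including dates of events".
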